Information sheet and informed consent	
 - Eligible participants will be e-mailed an information sheet (Appendix B) and consent form (Appendix C). Participants can ask any questions about the study via e-mail. - The researcher will schedule a study visit day, leaving 30-minute gaps between participant groups. Participants may bring a maximum of nine guests aged 18 years or older to the restaurant. - As the guests did not yet receive an online information sheet and consent form, all participants will also be provided with information by the researcher and provide verbal consent. The researcher will answer any questions prior to the study. 				
Meal choice task	
 - Participants will be invited to visit the restaurant. They will be assigned in advance to either the control or experimental condition. Any guests will be in the same condition as the primary participant (i.e., participants will be randomised by table). They will also be given a participant number which they will be required to enter in any questionnaire they complete. 				
	
  
 Control condition	Experimental condition	
   
  
 - Participants will receive a standard menu without nutrient warning labels. 	 
 - Participants will receive a menu featuring a nutrient warning label next to items high in salt. Text at the bottom of the menu will read “[label image] indicates that the salt content of this item is higher than 50% of the daily recommended limit (6g per day). High salt 	
  
	Control condition	Experimental condition	
 - Participants will receive a standard menu without nutrient warning labels. 	
 - Participants will receive a menu featuring a nutrient warning label next to items high in salt. Text at the bottom of the menu will read “[label image] indicates that the salt content of this item is higher than 50% of the daily recommended limit (6g per day). High salt
Control condition	Experimental condition				

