A logistic regression will be performed to assess the odds of selecting a high salt meal in the labelled menu group, using the control menu group as the reference category. The same covariates as above will be included.

As some participants are likely to bring guests to the restaurant and guest tables are the unit of randomization, there may be clustering for outcome variables (i.e., the variation in PME and/or salt purchase/intake may be partially explained by table). We will test for clustering effects by comparing the within-table variability for outcome variables to the between-table variability. We will use the likelihood ratio test to ascertain the difference in likelihoods between the two. If this is statistically significant ($p < .05$) then there is enough evidence to suggest that there is a clustering effect of table groups eating together. If there is evidence of clustering then we will perform a series of linear mixed model analyses, with label condition as an independent variable, and table group as a random effect for primary and secondary outcomes.

Exploratory analyses

Linear regressions will be performed to assess differences in menu conditions in terms of later salt intake, and intake of other macronutrients. This is to examine whether individuals engage in any compensatory eating behaviour after seeing the labels (e.g., they are aware that they consumed a

high salt meal and therefore reduce their salt intake later in the day), or whether intake of other macronutrients (e.g., calories) is impacted. Again, the same covariates as above will be included.

Sensitivity

Sensitivity analyses will be conducted to test if results are the same after removing any participants that correctly guess the aims of the study (i.e., the effect of salt warning labels on food choice, or similar). If many participants identify the study aims (e.g., > 25%) we will examine if study aim awareness status moderates any effects of labelling by including this as a covariate (categorical) in analyses. Any deviations in findings from the main analyses will be reported.

Missing data

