We do not foresee missing data being a problem as when we design measures in Qualtrics all fields will require a response, and all data will be collected by a researcher during the restaurant visit. However, it is possible that some participants will not complete the online questionnaire to assess later intake after the restaurant visit. Any missing data for later nutrient intake will be imputed.

Multiple comparisons

The alpha will be set at .05 for primary and secondary outcome analyses. To adjust for multiple comparisons, the alpha for exploratory analyses alpha will be reduced to .01.

Sample size

The label in the present study (or a similar label) has not previously been tested in a real-world UK context, in terms of PME or food choice. A RCT examining the effects of 'high in' added sugar labels on PME found large effects ($d = 0.58 - 0.63$) (7). A meta-analysis on food labelling found a small effect ($OR = 0.65$, or $d = .24$) of warning labels in terms of reducing consumers' probability of selecting less healthy items (31). However, a RCT examining the effects of 'high in' sodium labels on salt (g) and 'high in' item choice found very small effects ($d = 0.03$ and 0.04 respectively) (9), but there are important methodological differences (e.g., menu size) between this study and the present study. The primary purpose of the present study is to examine PME, so we will therefore power the study for this primary outcome, but in doing so we will have reasonable power to detect small-medium effects for our secondary outcome (food choice).

In the present study, G power calculation indicates a minimum sample of 260 participants (130 per condition) will provide sufficient power (80%, two-tailed) to detect small-medium between condition effects ($d = 0.35$) of the salt warning label on PME, salt purchased, and salt intake using between-subject ANOVAs (as planned).

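### Whole tables are randomised, but for later salt intake and the other-nutrient outcomes the plan settles neither a table term nor the alpha, because it classes them as both secondary and exploratory

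*Combined protocol and SAP*

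**What the plan says.** Allocation is by table. The Meal choice task row of the Study flow says "participants will be randomised by table", and the Intervention section confirms that people seated together share a condition. A participant may bring up to nine guests, so a table can hold ten.

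The clustering paragraph, at the end of the Secondary part of the Statistical analysis, recognises the consequence: "guest tables are the unit of randomization, there may be clustering for outcome variables". Its illustration is that "the variation in PME and/or salt purchase/intake may be partially explained by table". A likelihood ratio test at p < .05 decides whether clustering is present. If it is, mixed models are fitted "with label condition as an independent variable, and table group as a random effect for primary and secondary outcomes".

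The Exploratory analyses heading comes next: "Linear regressions will be performed to assess differences in menu conditions in terms of later salt intake, and intake of other macronutrients". These models take the covariates already listed for the primary analysis: education, health motives, age and gender. Table is not among them.

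Under Multiple comparisons, "The alpha will be set at .05 for primary and secondary outcome analyses", while "the alpha for exploratory analyses alpha will be reduced to .01".

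In Measures, however, both Later salt intake and Other macronutrient intake (kcal, sugar and saturated fat) are subsections of Secondary outcomes. The next heading, Additional measures, comes only after them.

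**The concern.** When every member of a table is in the same arm, correlation between tablemates adds to the variance of the arm comparison. An ordinary regression that treats diners as independent misses that extra variance. Standard errors come out too small, confidence intervals too narrow, and the test rejects more often than its nominal level.

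The plan wants these analyses to show whether labels lead people to compensate later in the day, or shift intake of calories and other nutrients. It sets a stricter alpha for exploratory tests to limit false positives. A single-level model would undo some of that protection, by an amount that the plan gives no means of judging. Separately, an analyst cannot tell from the text which alpha applies to these four outcomes.

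**Working it through.** **Plan's own figure.** The Sample size section gives 260 participants (130 per condition) for d = 0.35, 80% power, two-tailed. At alpha .05 the normal approximation gives 129 per arm (258 in total). The t-based calculation gives 129.1, rounded up to 130 per arm (260 in total), with power 80.3%. The figure reproduces. It treats diners as independent, and no design effect appears in it.

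**Which rule applies to these outcomes?**

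| Reading | Status | Table term | Alpha |
|---|---|---|---|
| Statistical analysis, Exploratory analyses | exploratory | none stated | .01 |
| Measures, Secondary outcomes | secondary | only if the clustering test gives p < .05 | .05 |

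Neither reading guarantees a table term.

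**Error rate if the exploratory section is followed as written.**

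Inputs from the documents: alpha .01 (two-sided, as in the sample size text), about 260 diners, whole tables allocated 1:1, at most 10 per table. Inputs assumed because the documents do not give them: table size m and within-table correlation ICC.

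- Design effect: DE = 1 + (m − 1) × ICC
- True size of the nominal .01 test: 2 × [1 − Φ(2.576 / √DE)]

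Low end, m = 2, ICC = .05: DE = 1.05, √DE = 1.025, 2.576 / 1.025 = 2.51, size 1.2%.

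High end, m = 4, ICC = .3: DE = 1 + 3 × .3 = 1.9, √DE = 1.378, 2.576 / 1.378 = 1.87, size 6.2%.

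| Table size (assumed) | ICC .05 | .10 | .20 | .30 | .50 |
|---|---|---|---|---|---|
| 2 | 1.2% | 1.4% | 1.9% | 2.4% | 3.6% |
| 3 | 1.4% | 1.9% | 3.0% | 4.2% | 6.9% |
| 4 | 1.6% | 2.4% | 4.2% | 6.2% | 10.3% |
| 10 (the cap, for everyone) | 3.2% | 6.2% | 12.4% | 18.1% | 27.2% |

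Across tables of 2 to 4 and ICC .05 to .3, the correct standard error is √DE = 1.025 to 1.378 times the one an ordinary regression reports.

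**Simulation check.** 8,000 trials per setting, about 260 diners, tables randomised 1:1, no label effect, ordinary t-test at .01, ICC .05 to .3:

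- all tables of 2: 1.2% to 2.4%
- a mix of 1 to 4: 1.2% to 3.8%
- all tables of 4: 1.6% to 6.2%
- a mix of 1 to 10: 1.7% to 6.9%

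These agree with the formula.

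**Does the remedy work?** A second simulation used 6,000 trials per setting, with tables of 1 to 6 (mean 2.65) or 1 to 10 (mean 3.65) and ICC from 0 to .5. Table-clustered standard errors held rejection at 0.8% to 1.7%. In the same settings the unadjusted test reached 8.7% and 13.7% at ICC .5.

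**The case against.** The strongest reply is that the remedy already covers these outcomes. Measures lists them as secondary, and the mixed model is promised for secondary outcomes. The clustering paragraph speaks of outcome variables generally, with PME and salt purchase/intake named only in a parenthesis. The salt purchase, salt intake and meal-choice models are also first written without a table term and then modified by that paragraph, so silence in the exploratory sentence does not prove a deliberate exclusion.

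Much of this stands. A reader might infer that these outcomes will always be analysed as if tablemates were independent. The documents do not support that, because on the Measures classification the conditional remedy reaches them. What survives is that the only analysis instruction specific to these outcomes sits in a later, separate section with its own alpha and specifies plain regression. Even on the generous reading, the table term depends on a significance test.

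A reader might also infer that these are the outcomes most prone to clustering, because companions may share an evening meal. No section says that tablemates live or dine together, and later intake happens after they leave the restaurant, so its correlation could be lower than that of the lunch outcomes. Correlation in what is ordered is plausible, since the questionnaire asks about sharing, but its size is unknown.

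Finally, these are not primary outcomes, and the sample size and interim decision do not rest on them. That limits the consequence but does not resolve the contradiction.

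**Conclusion.** The concern holds as a contradiction in classification plus an unstated table term. For later salt intake, kcal, sugar and saturated fat, the plan does not settle whether the clustering remedy applies or whether alpha is .05 or .01. Analysed as the exploratory section states, the nominal .01 test is too liberal for any positive within-table correlation once tables hold more than one person.

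The size is conditional. It is about 1.2% to 6.2% under assumed tables of 2 to 4 diners and ICC .05 to .3, close to 1% for small tables or low ICC, and above 10% for larger tables with high ICC. A reader might pick out a narrower band, such as 2% to 8%, as the likely error rate. The documents do not support that: it requires a design effect between 1.23 and 2.16, and they give neither an ICC nor a table-size distribution from which to derive one.

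The point should be corrected before analysis. It does not affect the primary outcome.

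**What to change.** State one classification for later salt intake, kcal, sugar and saturated fat, and make Measures, Exploratory analyses and Multiple comparisons agree, so that one alpha follows.

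In place of the plain regressions, specify linear mixed models with label condition, the stated covariates (education, health motives, age, gender) and a random effect for table. Linear regression with table-clustered standard errors is an acceptable alternative. Specify the table term outright, so that it does not depend on the clustering test.

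The change takes a sentence or two and no new data, because the order form in Appendix D records table number and group size alongside study IDs. With 260 diners in tables averaging 2 to 4, there would be about 65 to 130 tables (260 / 4 to 260 / 2). The cost is wider confidence intervals for these outcomes if tablemates are correlated, which reflects the real uncertainty.

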To date, the impact of nutrient warning labels has not been tested in a real-world randomised controlled trial (i.e., in a restaurant), or in a UK context. Recent work suggests that UK consumers support the introduction of nutrient warning labels, and their PME was rated as significantly higher relative to a control label (QR code) (13). This study aims to test the effect of a menu featuring salt warning labels (design informed by previous work (13)) on perceived message effectiveness relative to a menu with no labels in a real-world restaurant environment. The study will also act as a pilot experiment for examining the impact of the salt warning label on food choice and subsequent salt intake in real-world conditions.

Primary objectives:

- To measure the PME of a menu featuring salt warning labels relative to a menu with no labels
- To measure label awareness, perceived knowledge gain, and perceived influence of the label on food choice

Secondary objectives:

- To identify whether there is an effect of the salt warning label on:
 - Food choice (label/no label)
 - Total salt selected
 - Total salt intake
- To examine support for the introduction of a salt warning label policy in the UK

Experimental design

The study will be a between-subjects randomised controlled trial design. The between-subject factor is the menu labelling. In the experimental condition, a nutrient warning label will be placed next to menu items that are high in salt. In the control condition, there will be no labels. The outcome will be (i) perceived message effectiveness, (ii) salt selected, label (y/n) selected, and salt intake. This will allow us to examine whether the salt warning label intervention impacts perceived message effectiveness and food choice relative to the control condition.

Participants and recruitment

Recruitment

Participants will be recruited via social media adverts (Facebook, Instagram), a database maintained by researchers at the University of Liverpool, and word of mouth. Interested participants will be asked to click a link which will take them to an online screening questionnaire (Appendix A). Participants can bring a maximum of nine guests to the restaurant. Guests will be pre-screened in advance to ensure eligibility. In pre-study instructions participants will be informed that any guests they bring will participate in the study.

Sampling

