PME will be measured using an adapted version of the UNC PME scale. The scale measures health concern, product attitude, and discouragement of product consumption (21). Participants will answer 3 PME questions using a Likert scale ranging from 1 – 5 anchored by “not at all” and “a great deal”: Prompt: “Think back to the menu that you ordered from...” “The menu made me concerned about the health effects of consuming items high in salt”, “The menu made consuming items high in salt seem unpleasant”, “The menu discouraged me from wanting to consume items high in salt”. The mean response to the three items will be calculated. PME is used as an early indicator of a health message’s potential to change behaviour (e.g., reduce selection of items high in salt) (22). The scale has been used extensively in similar experiments to identify the potential impact of nutrient warning labels, has strong construct validity, and is predictive of longer-term actual behaviour (21, 23-28).

An attention check will be placed after the PME questions. “This question is an attention check, so please answer truthfully. How many times have you visited the planet Mars? Several times / Just once / Never”.

Correct answer: Never

Label awareness

"Did you notice any warning labels next to any of the menu items when making your meal selection?" (yes/no).

If [yes], "What did the label tell you about?" Response options: Healthy items, Organic, Calcium, Sustainable, Added sugars, Vegetarian, Unhealthy items, Salt, Fibre, Gluten Free, None of these, Not sure.

If [yes], "Please describe what the label said" (open text response). Responses that mention high in salt or similar will be coded as aware.

Salt awareness

"Did you think about the salt content of the meals when making your selection?" (yes/no)

Note: For the below questions, both groups will be shown an image of the labelled menu. Some question phrasing is slightly altered for the control condition.

Perceived knowledge gain

"Did you learn something new from the salt labels on the menu?" (yes/no).

Control: Same as above

Perceived influence

"Did the salt label influence which food you ordered from the menu" (yes/no).

"If [yes], how did the salt label influence your choice?" Response options: I avoided choosing a meal high in salt; I chose a meal high in salt; Other (free text response)

Control: "Would the salt label have influenced what food you ordered from the menu?" (yes/no)

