Participants will receive a link to a dietary recall questionnaire (Intake24, <https://intake24.co.uk/>) via email the next morning after taking part in the study, which they will be prompted to complete before midnight that day. They will be asked to provide as much detail as possible on what they had for dinner, snacks, and drinks after the restaurant visit. Based on this information and salt values calculated by Intake24, we will estimate the total salt consumed by the participants for the rest of the day after the visit.

Other macronutrient intake

Total kcal, sugar, and saturated fat intake [i.e., other nutrients that are not the main warning focus] will be calculated based on the nutritional content of the order of the participant.

Additional measures

Food choice motives

The “health” subsection of the Food Choice Questionnaire (29) will be used to measure the extent to which health motives may influence participants’ food choices. The subsection consists of 6 items, e.g. “It is important to me that the food I eat on a typical day....is nutritious” answered on a 4-point Likert scale ranging from “Not at all important” to “Very important”. We will calculate the mean response for the six items.

Aim guessing

Participants are told that the study is about dining habits in restaurants. At the start of the post-meal assessments, participants will be asked what they think the aims of the study were (free text response). Any participant that guesses the study aims to be investigating the influence of food warning labels on food choice will be coded as being aware of study aims. One researcher will code awareness of aims ([name]) and a second researcher will independently verify the coding.

Study flow

Recruitment	
 - Participants will be recruited via online adverts, word of mouth, and an existing participant database maintained by researchers at the University of Liverpool. - A link to the screening questionnaire will be provided. (Appendix A) - Participants will be stratified by SEP, age, and sex. 				

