Reimbursement	
 - Participants will receive £25 which will likely cover their lunch costs and serve as an incentive for people from different SEP strata to participate. Participants will either (i) pay for their own meal at the restaurant and receive £25 via invoice or (ii) have their meal paid for by a researcher using a prepaid card; if this costs less than £25, they can request to receive the remaining amount via invoice, if this costs more than £25, they will need to pay the difference at the restaurant. 	

Statistical analysis

Participant characteristics

Participant characteristics will be presented overall and by experimental condition in a table. Data will include age, gender, ethnicity, highest educational qualification, employment status, BMI, frequency of eating OOH, and hunger. Continuous variables will be summarised as means and standard deviations, and categorical variables will be summarised as counts and percentages.

Measured variables

Primary

A linear regression will be used to assess differences between menu conditions in terms of PME. The between-subjects predictor will be label condition, and the dependent variable will be PME.

Highest education level (categorical: NQF level 4 or above, NQF level 3 or below) will be included as a covariate in the model to account for stratification (30). Health motives (continuous) will be included as a covariate as this may predict outcomes (e.g., health motivated individuals may be more likely to believe a menu with labels will change their behaviour) (30). Age and gender will also be included as covariates as previous work suggests that this can influence ratings of label PME and salt intake (13).

Descriptive analysis will be used to report (overall and by condition) participants' label awareness, salt awareness, perceived knowledge gain, perceived influence, and policy support (dichotomised into support/oppose). Logistic regressions will be performed to assess the odds of (i) being aware of the label, and (ii) being aware of the salt content of the meals in the labelled menu group, using the control menu group as the reference category. The same covariates as above will be included.

Secondary

Linear regressions will be performed to assess differences in menu conditions in terms of total salt purchase and total salt intake. The same covariates as above will be included.

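### The sensitivity analysis that drops participants who guess the study aim is an arm-dependent, post-randomisation exclusion, so its result cannot show whether the main findings are robust.

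*Combined protocol and SAP*

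**What the plan says.** The Sensitivity paragraph plans to repeat the analyses after "removing any participants that correctly guess the aims of the study" and to report any departure from the main findings. It describes a correct guess as "the effect of salt warning labels on food choice, or similar". The Aim guessing paragraph (Additional measures) gives the coding rule: a participant counts as aware who "guesses the study aims to be investigating the influence of food warning labels on food choice".

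Four features of the design determine who can meet that definition:

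- Cover story, the same in both arms: "Participants are told that the study is about dining habits in restaurants".
- Exposure (Experimental design): "In the control condition, there will be no labels".
- Timing (Aim guessing): "At the start of the post-meal assessments, participants will be asked what they think the aims of the study were". Appendix E agrees. The aim question is the first substantive item, ahead of the salt-worded PME items.
- Later exposure of controls (Measures): "both groups will be shown an image of the labelled menu". In Appendix E this image comes well after the aim question.

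If more than about a quarter of participants guess, the plan adds awareness to the models as a categorical covariate to see whether it moderates the label effect. The plan does not provide for guess rates by arm.

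**The concern.** A sensitivity analysis on aim guessing would normally ask whether the result is produced by people who saw through the cover story. For deletion to answer that, guessing would have to be unrelated to the arm, or at least to how the intervention works. Neither can be expected here. Controls get no label cue from the menu or the questionnaire before they guess. Labelled diners get one from the menu itself. The plan treats noticing the label as an outcome to compare between arms: "Logistic regressions will be performed to assess the odds of (i) being aware of the label".

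Aim awareness is thus measured after randomisation, is affected by the arm, and is tied to noticing the label. Deleting on it leaves labelled diners selected for not having connected the label with the study, compared with nearly all controls. That comparison is no longer randomised. A smaller estimate could reflect removal of people who were merely playing along, or removal of people who engaged with the label as intended. An unchanged estimate is no clearer. The paragraph gives no rule for telling these apart, so a reader of the results could be misled about robustness in either direction.

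**Working it through.** **1. The plan's own figure.** Sample size section: d = 0.35, two-sided alpha 0.05, 80% power, 1:1 allocation, 260 participants. The normal approximation gives 129 per arm (258); the t-based calculation gives 129.1, hence 130 per arm (260). The stated figure reproduces. Power at 130 per arm is about 80%.

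**2. Assumed inputs.** The documents give none of these, so ranges are used:

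- q, share of the labelled arm noticing the label: 0.4 to 0.8
- g, share of noticers who guess the aim: 0.25 to 0.75
- c, share of controls who guess: 0 to 0.05

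Clustering by table and covariate adjustment are ignored.

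**3. Who is removed.** Labelled arm: 130 × q × g, from 130 × 0.4 × 0.25 = 13 to 130 × 0.8 × 0.75 = 78. Control arm: 130 × c, from 0 to 6.5. The labelled share of all deletions is qg/(qg + c). Its lowest value is 0.10/(0.10 + 0.05) = 67%; its highest is 100%, when c = 0.

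**4. Estimate after deletion if the label acts only in noticers.** With an overall effect of 0.35, the effect in noticers is 0.35/q. After deletion a share q(1 − g)/(1 − qg) of the remaining labelled diners are noticers, so

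effect after deletion = 0.35 × (1 − g)/(1 − qg).

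| q | g | calculation | effect (SD) |
|---|---|---|---|
| 0.8 | 0.25 | 0.35 × 0.75/0.80 | 0.33 |
| 0.6 | 0.50 | 0.35 × 0.50/0.70 | 0.25 |
| 0.4 | 0.75 | 0.35 × 0.25/0.70 | 0.13 |

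The first and last rows are the extremes of the range. In the middle row with c = 0.02, 39 labelled and 2.6 control participants are removed, leaving 91 and 127.4. The standard error is √(1/91 + 1/127.4) = 0.137, and power is Φ(0.25/0.137 − 1.96), about 44%. Over the whole range, power falls from about 80% to between 70% and 15%, with nothing wrong in the main result.

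**5. Uniform effect.** If every labelled diner has the same effect and guessing is unrelated to the outcome, deletion changes sample size only. The expected estimate stays at 0.35.

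**6. No label effect, but guessers differ anyway.** Suppose a share p of the labelled arm guesses, no controls do, and guessers score b SD higher for reasons unrelated to the label. The remaining labelled mean shifts by −p × b. With p = 0.30 and b = 0.3 this is −0.09 SD; over p = 0.15 to 0.45 and b = 0.2 to 0.5 it runs from −0.03 to −0.225 SD. If guessers score lower, the sign reverses. The planned health-motives covariate would absorb some of this only if the difference comes through health motives.

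**7. The over-a-quarter step.** With equal arms, 25% overall requires a labelled-arm rate of 0.50 − c: 50% if no controls guess, 45% if 5% do. Awareness is then close to a subset of the labelled arm. At c = 0.02 there would be 2.6 aware controls out of 130.

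**8. Trimming bounds, if wanted.** Example: 30% aware in the labelled arm, 2% in control, effects assumed to be 0.75 SD in aware and 0.15 SD in unaware diners. The overall effect is 0.30 × 0.75 + 0.70 × 0.15 = 0.33. The excess to trim from the remaining controls is 1 − 0.70/0.98 = 0.286, about 29%. For a normal outcome, trimming that share from one tail shifts the control mean by φ(0.566)/0.714 = 0.340/0.714 = 0.48 SD. The bounds are 0.15 ± 0.48, or −0.33 to +0.63 SD.

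**The case against.** The strongest reply has four parts.

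*No main estimate is touched.* This stands. Deletion is confined to the Sensitivity paragraph, and neither the main analyses nor the interim decision uses it. A reader might infer that the primary PME result is biased; the documents do not support that.

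*Noticing is not strictly required to guess.* This also stands. A reader might infer that only labelled diners can be coded aware. But the Sensitivity wording leaves room for near matches, and word-of-mouth recruitment gives controls a route to the aim. Conversely, a labelled diner can notice and respond to a label without inferring the study's purpose. The right word is mainly.

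*Attenuation is assumed, not shown.* Largely right. A reader might infer that deletion must shrink the effect. Step 5 shows it need not, and an example that assigns a large effect to aware diners and a small one to the rest only hands back its inputs when the aware are removed. What survives is that the direction and size of any change cannot be interpreted.

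*The plan never says a change will be read as a demand effect.* True; it promises only to compare and report, and label awareness is already to be described by condition. But a test of whether results are the same, with no statement of what a difference means, leaves that reading open. The covariate step for high guess rates does not help. A main effect of awareness does not test moderation, and with so few aware controls an interaction could hardly be estimated.

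**Conclusion.** The point holds as a flaw in the stated robustness check, not in the main analysis. It follows from three features of the plan: the guess is taken after the meal, only one arm has by then seen labels, and a correct guess must concern warning labels. It does not depend on any assumed rate.

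The size does. Over the ranges in the working, 67% to 100% of those deleted come from the labelled arm. If the label acts only through noticing, an overall effect of 0.35 SD becomes 0.33 to 0.13 SD. With a uniform effect and guessing unrelated to the outcome there is no attenuation. The documents do not allow a choice between these cases, so neither a changed nor an unchanged estimate supports a conclusion about robustness or demand effects.

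**What to change.** In the Sensitivity paragraph:

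1. State that conclusions on PME and food choice rest on all randomised participants.
2. Tabulate aim awareness by arm, beside label awareness.
3. If an analysis without guessers is kept, label it descriptive and non-randomised, and say that a difference from the main result will not be read as evidence for or against robustness or demand effects. Give the covariate step for high guess rates the same label, and do not describe it as a test of moderation.

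Trimming bounds are optional. If used, trim the control arm by the excess deletion fraction (about 29% of remaining controls in the 30% versus 2% example), once from each end of the outcome. Expect a wide range: about 1 SD in that example, against a design effect of 0.35. The bounds concern diners who would not guess even if labelled. They do not recover the all-randomised effect or separate demand from label effects.

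Cost: a few lines of text and one table row, with no new data. The downside is that the plan loses a single-number robustness check.
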